6. STATISTICAL CONSIDERATIONS

Analysis of outcome measures

The primary research hypothesis for the trial is that a reduced volume of post-operative radiotherapy treatment for adult extremity soft tissue sarcomas will improve limb function without compromising local control. Secondary research hypotheses are that the reduced treatment improves toxicity, overall level of disability and is not inferior to the standard treatment in terms of disease-free survival and overall survival.

The primary analysis for the trial is to compare the experimental treatment to the control treatment in terms of benefit to limb function and non-inferiority for time to local recurrence. For limb function, TESS will be analysed using longitudinal statistical methods, in particular summary measures analysis. The two treatment groups will be compared in terms of TESS at 2 years and area under the curve using either t-tests or Wilcoxon tests depending on the distribution of the data. The proportion of patients in each treatment arm who report small, medium or large change (with worsening or improvement reported separately) between each assessment interval will be required. For time to local relapse, statistical analysis will be based on a one-sided 95% confidence interval for the hazard ratio and non-inferiority will be inferred when the entire confidence interval falls above the non-inferiority margin of 0.63 (equivalent to a difference of 80% versus 70% in 2-year local relapse-free rates).

The rates of grade 3 or 4 toxicity on the two treatment arms will be compared using chisquare tests. Overall level of disability will be analysed using longitudinal statistical methods similar to those used for TESS. Statistical analysis for disease-free survival and overall survival will be based on one-sided 95% confidence intervals for the hazard ratio to assess non-inferiority.

Interim analysis

Interim analyses will be carried out annually and presented to an independent Data Monitoring Committee (DMC). The interim analyses will present recruitment data and data on all primary and secondary outcomes.

Final analysis

The study is expected to complete recruitment within 4 years. Final analysis will be carried out after all patients have been followed up for a minimum of two years.

Calculation of sample size

Sample size calculations are based on the two primary outcome measures of limb function and time to local recurrence. In relation to limb function, a difference in TESS score between the two treatment arms of 10 points would indicate a clinical benefit to patients (Davis, personal communication). Previous data has suggested an expected standard deviation for the score of 20. The key analysis for this outcome measure is the difference in score at two years. Assuming a null hypothesis of no difference will be tested using a t-test with 5% significance level and assuming a standard deviation of 20, 105 patients per treatment arm will be needed to detect this size of difference at two years with 95% power.

In relation to local relapse, sample size is calculated based on showing that the 2-year local relapse rate on the experimental treatment arm is non-inferior to that on the control arm. The two-year local relapse-free rate on the control treatment is expected to be 80% and a decrease in this rate to 70% would be the largest difference between treatments that can be judged as clinically acceptable. A non-inferiority margin of 70% is therefore chosen as relevant for this trial. With 198 patients per arm with full follow-up for two years and using a one-sided 95% confidence interval there will be 80% power to detect non-inferiority in two-year local relapse-free rates of 10% or less.

In conclusion, with 200 patients per treatment arm, there will be 95% power to detect a difference of 10 points in the TESS score between the treatment arms at two years and 80% power to determine non-inferiority in local relapse-free rates with non-inferiority defined as a difference in two-year local relapse-free rates of 10%.

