7. STRATIFICATION

Patients will be stratified by tumour grade, adequacy of surgical clearance and centre.

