Appendix 4: Toronto Extremity Salvage Score (TESS) - Lower Extremity

VonteX	PATIENT	DEMOGR	APHIC IN	FORMATION FOR	М
	TORO	NTO EXT	REMITY S	ALVAGE SCORE	
	Patient's Initials:		Reg No.	TNO	
Please	e complete the foll	owing que	stions:		
1.a. Please sta	te your current work s	tatus:			
Employed	full-time				
Employed	part-time				
Unemploy	ed				
Retired					
Student					
Disabled					
1.b. If you are o	employed, please give	your currer	nt job title:		
Re-code:	1 Active	2 Se	dentary		
1.c. Briefly des	scribe your leisure or r	ecreational	activities (e	xamples: sports, gard	dening, reading):
Re-code:	1 Active	2 🖂 S	edentary		
Ne-code.	Active	² 🗀 ³	ederitary		
2 a Are vou re	gularly taking pain me	dication:			
None	gularry taking pain me	dication.			
	.g. Ibuprofen				
=		Co dudesas			
	illers e.g. Paracetamol,	Co-dydramo	4		
Strong pai	n killers e.g. Morphine				
Page 1 of 11					
Cancer Research UK T	rials Unit, Birmingham			Lower Extremity TESS Form	. Version 2.0 24/04/2009

PATIENT DEMOGRAPHIC INFORMATION FORM

TORONTO EXTREMITY SALVAGE SCORE

	Patient's Initials: Reg No. TNO
2.b.	Frequency of pain medication:
	Not applicable i.e. no medication Intermittent Once a day Twice a day 3 times or more a day
3.	Describe the mobility or walking aid you use:
	No aid
	One cane or crutch
	Two canes
	Two crutches
	Walker
Ļ	Wheelchair
	Motorised wheelchair or scooter
4.	List the factors that limit your ability to perform your everyday activities:
	None
Ļ	Pain
	Stiffness Fatigue
	Weakness
	Other (please specify below)

Page 2 of 11

Cancer Research UK Trials Unit, Birmingham

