Appendix 4: Toronto Extremity Salvage Score (TESS) - Upper Extremity

Von Ed X PATIENT DEMOG	RAPHIC INFORMATION FORM
TOPONTO EVI	DEMITY CALVACE COOR
 	REMITY SALVAGE SCORE
Patient's Initials: Reg N	io.
Please complete the following que	stions:
1.a. Please state your current work status:	
Employed full-time	
Employed part-time	
Unemployed	
Retired	
Student	
Disabled	
1.b. If you are employed, please give your curren	t job title:
Re-code: 1 Active 2 Sec	dentary
1.c. Briefly describe your leisure or recreational	activities (examples: sports, gardening, reading):
Re-code: 1 Active 2 Sec	dentary
2.a. Are you regularly taking pain medication:	
None	
NSAIDS e.g. Ibuprofen	
Mild pain killers e.g. Paracetamol, Co-dydramo	I
Strong pain killers e.g. Morphine	
outrig pair miles e.g. morphise	
Page 1 of 11	
Cancer Research UK Trials Unit, Birmingham	Upper Extremity TESS Form. Version 2.0. 24/04/2009

Vonte	X PATIENT DEMOGRAPHIC INFORMATION FORM TORONTO EXTREMITY SALVAGE SCORE Patient's Initials: Reg No. TNO TO
Not ap	a day
3. Are you Left ha Right h	anded
None Pain Stiffne: Fatigue Weakn	e

Page 2 of 11

Cancer Research UK Trials Unit, Birmingham

Vonte	X UPPER EXTREMITY
	TORONTO EXTREMITY SALVAGE SCORE
	Patient's Initials: Reg No. TNO

ark each item (a rform each tas	estions are about activities commonly performe (as in the examples below) opposite the descrip sk during the past week . Some activities will be It or impossible.	otion that best describes	your ability to
E	EXAMPLE		
P	Peeling vegetables is:		
1	Impossible to do Extremely difficult Moderately difficult A little bit difficult Not at all difficult This task is not applicable to me		
your daily acti pain. If you do not p indicate that t	thoose the response "impossible to do" if the a tivities but are now unable to do because of pl perform an activity as part of your normal lifesty the item is not applicable. s ensuring that you choose the description that	hysical limitations such a yle you would choose the	s weakness, stiffness, o e response *99* to
1 □	Putting on a pair of trousers is: Impossible to do Extremely difficult Moderately difficult A little bit difficult Not at all difficult This task is not applicable to me		

Page 3 of 11

Cancer Research UK Trials Unit, Birmingham

Von	ŧέΧ	U	PPER EXTREMITY		
	TOF	RONTO	EXTREMITY SALVA	GE SCO	RE
•	Patient's Initials:		Reg No.	TNO	
	-				
2. 1	Tying shoe laces is:				
1	Impossible to do				
2	Extremely difficult				
3	Moderately difficult				

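### Upper- and lower-limb patients answer different TESS forms (13 shared items), but section 6 compares pooled scores with no limb term; the test stays valid, and adding limb would be a nearly free gain in precision and clarity

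*Protocol*

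**What the plan says.** Limb function measured by TESS is one of two primary outcomes (section 2). Section 3 describes it as a single patient-completed score from 0 to 100, and section 4 admits tumours of either extremity.

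The instrument comes in two versions: "Appendix 4: Toronto Extremity Salvage Score (TESS) - Lower Extremity" and "Appendix 4: Toronto Extremity Salvage Score (TESS) - Upper Extremity".

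For the analysis, section 6 states: "The two treatment groups will be compared in terms of TESS at 2 years and area under the curve". The tests named are t-tests or Wilcoxon tests, chosen by the distribution of the data. The sample size rests on one target and one spread for all patients: "a difference in TESS score between the two treatment arms of 10 points would indicate a clinical benefit to patients", and "Previous data has suggested an expected standard deviation for the score of 20".

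Section 7 says: "Patients will be stratified by tumour grade, adequacy of surgical clearance and centre". Limb is not in that list. No limb term, limb-stratified test or limb-specific report appears anywhere in the protocol.

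**The concern.** A score of, say, 80 on the lower-limb form summarises mostly kneeling, stairs, standing and walking. The same score on the upper-limb form summarises mostly buttoning, writing, lifting and turning a key. The protocol offers nothing to show that the two scores are interchangeable, yet the tests it names treat them as one scale.

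Two things follow. If mean scores differ between the forms, that difference adds to the error variance of a comparison that ignores limb. And if the rank test is chosen, many of the pairwise comparisons that it is built from set an upper-limb patient against a lower-limb patient. The pooled estimate alone also does not show whether a benefit is seen in legs, in arms or in both.

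This is a stated method, not a silence left to the analysis plan: section 6 names the tests, and they are unadjusted two-sample tests. Adjusting for the existing stratification factors would not help, because limb is not among them.

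**Working it through.** **Item overlap (Appendix 4).** The lower form has 30 scored items and the upper form 29. Thirteen match: trousers, socks or stockings, showering, light chores, gardening, meals, shopping, heavy chores, usual work duties, usual working hours, leisure, socialising and sport. Light chores, heavy chores and meals differ slightly in wording; the other ten are the same. That leaves 30 - 13 = 17 lower-limb and 29 - 13 = 16 upper-limb items without a direct counterpart, although putting on shoes and tying laces are close. General questions A and B are the same on both forms, so the secondary disability outcome is not affected.

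**Reproducing the plan's figure.** Inputs from section 6: difference 10, SD 20, power 95%, and a null hypothesis that "will be tested using a t-test with 5% significance level". Sidedness is not stated; I take two-sided.

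- Normal approximation: n = 2 × (1.960 + 1.645)² × 20² / 10² = 103.96, so 104 per group.
- Two-sample t-test (noncentral t): 104.93, so 105 per group, with 95.0% power.

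This agrees with the protocol: "105 patients per treatment arm will be needed to detect this size of difference at two years with 95% power".

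**Assumptions.** The documents do not give the upper-limb share p or the mean gap d between forms. I take p = 20-40% and d = 0-15 points.

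**Reading A: 20 is the SD within a limb.** Pooled variance without a limb term = 400 + p(1 - p)d². N is by the normal approximation; power is for the t-test.

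| p, d | Variance | SD | N per group for 95% power | Power at 105 | Power at 200 |
|---|---|---|---|---|---|
| any, 0 | 400 | 20.00 | 104 | 95.0% | 99.88% |
| 0.2, 5 | 404 (+1.0%) | 20.10 | 105 | 94.8% | 99.87% |
| 0.3, 10 | 421 (+5.3%) | 20.52 | 110 | 94.0% | 99.81% |
| 0.4, 15 | 454 (+13.5%) | 21.31 | 118 | 92.3% | 99.68% |

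**Reading B: 20 is already the overall SD.** A limb term lowers the residual variance to 400 - p(1 - p)d². This is 396 (SD 19.90, N 103) at p = 0.2, d = 5, and 346 (SD 18.60, N 90) at p = 0.4, d = 15. Nothing planned is lost; the term only gains precision.

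**Validity.** In 10,000 simulated trials per setting (30% upper limb, 10-point gap, within-limb SD 20), type I error of the pooled t-test and Wilcoxon test was 4.8-5.3% at 105 and 200 per group. Power at 105 per group was 94.0% (t-test), 92.9% (Wilcoxon) and 94.7% (limb-adjusted).

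**Chance imbalance in limb.** Its 95% range of shift in the estimate is 1.96 × d × √(2p(1 - p)/n). At 200 per group this is 0.39 points (p = 0.2, d = 5) to 1.44 points (p = 0.4, d = 15); at 105 it is 0.54 to 1.99. It is not an extra harm on top of the variance above. At 200 per group the ordinary 95% half-width is 1.96 × 20 × √(2/200) = 3.92. Combining, √(3.92² + 1.44²) = 4.18, which is what the pooled variance gives directly: 1.96 × √(2 × 454/200) = 4.18.

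**Cross-limb pairs in a pooled rank test.** The expected share of between-group pairs that cross limbs is 2p(1 - p): 32% at p = 0.2 and 48% at p = 0.4.

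**The case against.** The strongest reply is that nothing is broken. The comparison is between randomised groups, limb is fixed before randomisation, and the pooled test has the right error rate. At the planned 200 per group, power hardly moves. Covariates, stratified rank tests and per-limb tables often belong in the analysis plan, and section 6 does not forbid them. The inputs that drive the size are assumed; with no gap between forms the quantified loss is zero. Both forms also share the same response options, including one for tasks that do not apply, so even patients on the same form may be scored on different items. Partial overlap alone does not show that pooling is wrong.

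Most of this stands, and it limits the weight of the point. What remains is that section 6 does name unadjusted two-sample tests and sets aside a strong candidate covariate that is known for every patient.

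Three stronger readings are tempting, and the documents do not support them:

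- A reader might infer that chance imbalance in limb biases the result. It does not; it is part of the variance that the standard error already covers.
- A reader might infer that the TESS comparison is underpowered. That does not follow at 200 per group, and at 105 the loss is at most about 3 percentage points under these assumptions.
- A reader might infer that a limb term makes the two forms commensurable. It removes a mean difference, but the pooled effect still averages points from two instruments, and the documents hold no evidence on equivalence either way.

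Section 5 also allows patients with the brachial plexus in the treated volume to be left out of the final analysis. That is a separate matter: the validity stated here is for the randomised groups kept whole, and a limb term would not generally repair bias from such exclusions.

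**Conclusion.** The point holds as an improvement in precision and interpretability, not as a flaw that invalidates the TESS comparison. Two forms with 13 shared items are analysed as one score, without limb in the randomisation or the analysis. With a 20-40% upper-limb share, a 0-15 point gap and 20 read as the within-limb SD, the cost is 0-13.5% more variance. Power is then no lower than about 92% at 105 evaluable patients per group and about 99.7% or more at 200. If 20 is the overall SD, there is no loss against plan, only precision forgone. The clearest gain is in interpretation: under those shares, 32-48% of pairs in a pooled rank test would no longer cross instruments, and readers would see the effect in each limb. Share and gap are assumptions throughout.

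**What to change.** In section 6, state that:

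1. The comparisons of two-year TESS and of area under the curve include limb (upper or lower form) as a factor, in a linear model with treatment group and limb.
2. If a rank test is used, it is stratified by limb (van Elteren), so that scores are ranked only within the same form.
3. The treatment effect and its confidence interval are reported for each limb beside the pooled estimate, as description only. At 200 per group, a 20-40% upper-limb share leaves 40-80 upper-limb patients per group. The 95% half-width at SD 20 is then 1.96 × 20 × √(2/40) = 8.8 down to 1.96 × 20 × √(2/80) = 6.2 points, too wide for separate conclusions.
4. The limb term does not itself establish that a 10-point difference means the same on both forms.

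If the analysis plan already does this, section 6 should be brought into line with it.

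The cost is a few sentences and one degree of freedom. Limb is known before randomisation for every patient, so sample size, data collection and randomisation are unchanged.

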 carcinoma of the cervix) within the last 3 years.

Investigations required prior to randomisation:

- Haematology: FBC with differential
- Radiology: chest X-ray, CT thorax and MRI local site
- Wound assessment
- Completion of the Toronto Extremity Salvage Score questionnaire
- Completion of the Patient Perceived Change of Status guestionnaire

National Trial Co-ordinator details:

Name: [name], VORTEX Trial Co-ordinator

Cancer Research UK Clinical Trials Unit, Institute for Cancer Studies, University of Birmingham, [name]

[name]

[contact] [contact] E-mail: [contact]

TABLE OF CONTENTS

1. INTRODUCTION	9
BACKGROUND	9
Adjuvant Radiotherapy	
Surgical margins and radiotherapy dose	
RATIONALE	12

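### The co-primary TESS comparison is an unadjusted t-test or Wilcoxon test chosen from the data, so it gives up precision that the pre-randomisation TESS and the stratification factors could supply

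*Protocol*

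**What the plan says.** TESS is one of two primary outcomes. In section 6, Analysis of outcome measures, the approach is described as "TESS will be analysed using longitudinal statistical methods, in particular summary measures analysis". The arms are then "compared in terms of TESS at 2 years and area under the curve using either t-tests or Wilcoxon tests depending on the distribution". No baseline score, stratification factor or other covariate is named for this comparison, and no criterion is given for choosing between the two tests.

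In the same section, Calculation of sample size is more definite. It says "The key analysis for this outcome measure is the difference in score at two years" and continues "Assuming a null hypothesis of no difference will be tested using a t-test with 5% significance level". The planning values are also there: "a difference in TESS score between the two treatment arms of 10 points would indicate a clinical benefit to patients", and "Previous data has suggested an expected standard deviation for the score of 20".

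TESS is available before allocation. The study summary lists "Completion of the Toronto Extremity Salvage Score questionnaire" among the investigations required before randomisation. The schedule of events places TESS before surgery and at the post-operative oncology appointment, and the trial schema puts both ahead of randomisation. It is repeated at 3, 6, 12, 18 and 24 months after the operation. Section 7 adds: "Patients will be stratified by tumour grade, adequacy of surgical clearance and centre".

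**The concern.** The protocol collects a pre-randomisation value of the primary outcome, and stratifies the allocation, but the stated analysis uses neither. When a baseline score predicts the two-year score, leaving it out widens the interval. Ignoring stratification factors that predict outcome also tends to make the reported standard error larger than it need be.

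There is a smaller second issue. A t-test addresses a difference in means; a Wilcoxon test compares ranks and gives no estimate of the 10-point mean difference that the protocol calls a clinical benefit. Letting the observed distribution decide leaves the reported quantity open until the data are seen.

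At stake is the width of the interval on a co-primary outcome, and a clear statement of what that interval estimates.

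**Working it through.** **Inputs from section 6, Calculation of sample size:** difference 10 points, SD 20, 5% level, 95% power, 105 per arm stated for TESS, 200 per arm planned. The correlation r between baseline and two-year TESS is not given; r = 0.3 to 0.6 is an assumption.

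**1. The protocol's own figure.** By the normal approximation, n per arm = 2 × (1.960 + 1.645)² × 20² / 10² = 2 × 13.0 × 4 = 104. The exact two-sided t-test gives 104.93, so 105. The stated figure reproduces. A one-sided test would give 87, so the 5% level is evidently two-sided.

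**2. Power at the planned size, unadjusted.** SE = 20 × √(2/200) = 2.00. Then 10/2.00 − 1.96 = 3.04, which gives power of about 99.9%. Power stays at 95% until only 105 of 200 forms per arm remain, that is, until 1 − 105/200 = 47.5% are missing.

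**3. Effect of adjusting for baseline.** Residual SD = 20 × √(1 − r²); SE = residual SD × √(2/200); 95% half-width = 1.96 × SE; equivalent gain in patients = 1/(1 − r²) − 1.

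| r (assumed) | Residual SD | SE at 200 per arm | 95% half-width | n per arm for 95% power | Equivalent gain |
|---|---|---|---|---|---|
| unadjusted | 20.00 | 2.00 | 3.92 | 104 (105 exact) | – |
| 0.3 | 19.08 | 1.91 | 3.74 | 95 | 10% |
| 0.5 | 17.32 | 1.73 | 3.39 | 78 | 33% |
| 0.6 | 16.00 | 1.60 | 3.14 | 67 | 56% |

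The difference detectable with 95% power at 200 per arm is 3.605 × SE: 7.2 points unadjusted, 6.9 at r = 0.3 and 5.8 at r = 0.6. Any further gain from the stratification factors is not counted, because the protocol gives nothing from which to size it.

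**4. Choosing the test from the data.** Two groups of 200 were simulated 10,000 times with no difference, on a skewed 0–100 score with SD about 20. A pre-specified switch on a Shapiro test rejected in 5.1% of runs. That equals the Wilcoxon test's own rate in these runs, so they say little about distributions nearer to normal. Taking the smaller of the two p-values rejected in 6.9%.

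**5. Two summaries, conditionally.** If TESS at two years and AUC were each tested at 5%, and either could support the claim, the chance of at least one false positive would be 7.0% at a correlation of 0.9 and 8.8% at 0.6. This counts both directions. A false claim of benefit would be about half of that, 3.5% to 4.4% against 2.5%.

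**The case against.** The strongest objection is that the loss has little practical consequence. The trial's size is set by local relapse, which needs 198 per arm, while TESS needs 105. Power for TESS is close to 100%, and even the unadjusted half-width of 3.92 points is small against a 10-point target. An unadjusted comparison of randomised groups is valid, and its standard error already allows for chance baseline imbalance. All of this stands. It limits the point to precision, but it does not remove a gain that needs no new data.

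A second objection is that the sample-size text already names the two-year difference as the key analysis and plans a t-test. That largely settles which summary leads. A reader might infer from the analysis text that there are two routes to a positive TESS result, with a false-positive rate of 7.0% to 8.8%. No section says that either summary may count, so that range is only conditional. Likewise, the 6.9% for the better of two p-values describes a practice that the protocol does not propose, and a switching criterion may stand in a statistical analysis plan that is not shown.

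A reader might also infer that patients without a 24-month form are excluded, so that the arm with worse local control is flattered by its survivors. The protocol does not say this. A two-sample test at two years can use only patients with a score, but that follows from the method, and AUC might retain earlier visits. No section stops TESS at recurrence, and section 13 keeps patients who leave trial treatment in data collection unless they specify otherwise. An arm with worse local control must also pass the other primary comparison.

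**Conclusion.** The point holds as a matter of precision and of fixing one analysis. The protocol itself states the unadjusted method, so this is not merely a detail left for later. For an assumed baseline correlation of 0.3 to 0.6, adjustment would cut the standard error at 200 per arm from 2.00 to between 1.91 and 1.60 points, and the 95% half-width from 3.92 to between 3.74 and 3.14. The figures rest on the protocol's SD of 20 and on that assumed range; at the low end the gain is small.

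The documents do not support calling the test invalid, the trial underpowered for TESS or the type I error inflated, and they do not establish a survivor bias. The analysis text and the sample-size text should nevertheless be brought into line on which summary and which test are primary.

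**What to change.** In section 6, Analysis of outcome measures, state one primary TESS analysis: the difference in mean TESS at 24 months, two-sided 5%, in keeping with the key analysis named under Calculation of sample size. Estimate it by ANCOVA, or by a repeated-measures model on the post-randomisation scores. Adjust for pre-randomisation TESS, tumour grade, surgical clearance and centre (for example as a random effect). Upper or lower limb may be added, since the two questionnaires differ. Say which of the two pre-randomisation scores is the baseline; the post-operative one is nearer to randomisation. Make AUC and the rank test supportive.

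If a repeated-measures model is chosen, add a sensitivity analysis for deaths and for forms missing after recurrence. Missing-at-random is doubtful there, and the model does not by itself settle what a score means for a patient who has died.

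The cost is a change of wording and slightly more modelling, with the assumptions that it brings. No new data, visits or patients are needed, and the sample size is unaffected.

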A survey of international practice in terms of surgical margins and dose has been carried out and indicated that approximately 60% of clinicians applied a 5cm margin to the surgical scar when planning post-operative radiotherapy and the same margin to the tumour bed when planning pre-operative treatment (Robinson 1998 personal communication). Lindberg and Suit have previously recommended larger margins (7-15cm) depending on size and grade of tumour. There are very few studies in the literature looking at the target volume used when planning radiotherapy and this tends to be poorly reported. One group found a remarkable difference in 5-year local control where the margin was <5cm (30%) or >=5cm (93%) (Mundt 1995). This conflicts with the brachytherapy data where acceptable results are achieved using 4cm margins longitudinally and 2cm laterally. (Fein *et al*; 1995). This author also reported that local control was dose dependent. Fein 1995 noted that patients receiving <62.5Gy had 5-year local control of 78% v 95% where the dose was >62.5Gy. (Robinson *et al*; 1992) failed to demonstrate a variation in local control according to dose, although the response rate to pre-operative radiotherapy was clearly dose dependent.

It is common practice for clinicians to use a 'shrinking field' technique for the treatment of extremity sarcomas. A typical phase 1 dose is 50Gy in 25 daily fractions followed by a 10-16Gy boost in 5-8 fractions. A recent publication from the Royal Marsden Hospital has suggested that as in other tumour sites the great majority of local recurrences occur within the high dose volume (Cleator, 2001). This rises the question regarding the large volume phase 1 being necessary or if the boost is necessary where an adequate surgical margin has been achieved.

There is currently an influx of new radiotherapy techniques such as Intensity-Modulated Radiotherapy (IMRT) being introduced, which will permit the selective sparing of normal tissues. There is a need to accurately determine the volumes that can safely be spared before implementing these techniques. Prior to considering the implementation of IMRT techniques (Millar, 2001) it is important to obtain relevant and accurate dose/volume data, which can be collated with functional outcomes.

Rationale

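### Local recurrence is tested against a hazard ratio of 0.63, but non-inferiority is also defined as a 10-point difference, and the stated 80% power belongs only to that difference

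*Protocol*

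**What the plan says.** All the relevant text is in Protocol section 6.

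- **Analysis of outcome measures.** Local relapse is to be judged by a one-sided 95% interval on the hazard-ratio scale. The criterion reads: "non-inferiority will be inferred when the entire confidence interval falls above the non-inferiority margin of 0.63". A parenthesis explains the figure as "equivalent to a difference of 80% versus 70% in 2-year local relapse-free rates". The text does not say which arm's hazard is the numerator.
- **Calculation of sample size.** "The two-year local relapse-free rate on the control treatment is expected to be 80" per cent, and a fall to 70% is the largest loss judged acceptable. Then: "A non-inferiority margin of 70% is therefore chosen as relevant for this trial". With 198 per arm, each followed for two years, and a one-sided 95% interval, power is given as 80%. The closing summary, for 200 per arm, has "non-inferiority defined as a difference in two-year local relapse-free rates of 10" per cent.
- **Final analysis.** It takes place once every patient has at least two years of follow-up. Recruitment is expected to take four years.

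The protocol does not say which statement governs if the control rate is not 80%.

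**The concern.** A non-inferiority conclusion is only as clear as its margin. Here the test is on the hazard-ratio scale, while the sentence that defines non-inferiority is on the scale of a difference in two-year proportions. A ratio margin and a difference margin can agree at only one control rate, and the 80% is an expectation.

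Two things are at stake. First, if the control arm does better or worse than 80%, the verdict on local control may depend on which sentence of section 6 is followed. Second, the trial is described as having 80% power for non-inferiority. If that figure was worked out for the difference, it does not describe the analysis that will be done.

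**Working it through.** **Inputs (Protocol section 6).** Control rate 80%, lowest acceptable rate 70%, one-sided alpha 0.05 (z = 1.645), power 80% (z = 0.842), 198 or 200 per arm, hazard-ratio margin 0.63.

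**1. Reproduce 0.63.** Under proportional hazards, the control/experimental hazard ratio is ln(0.80)/ln(0.70) = 0.626, which rounds to 0.63. The inverse of 0.63 is 1.59.

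**2. Reproduce 198.** For a difference in proportions with both arms at 80% and a margin of 0.10:

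n = (1.645 + 0.842)² × (0.80×0.20 + 0.80×0.20) / 0.10² = 6.18 × 0.32 / 0.01 = 198 per arm.

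This is an exact match; power is 0.800 at 198 and 0.804 at 200.

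**3. Events needed by the hazard-ratio rule (Schoenfeld).**

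4 × 6.18 / (ln 0.63)² = 24.73 / 0.2135 = 116 events.

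The rule is driven by events, and the 198 does not come from it.

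**4. What each margin allows at other control rates.** The rate allowed by the ratio is (control rate)^(1/0.63).

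| Control rate | Drop allowed by 0.63 | Hazard ratio equal to a 10-point drop |
|---|---|---|
| 70% | 13.2 points | 0.698 |
| 75% | 11.7 | 0.668 |
| 80% | 9.8 | 0.626 |
| 85% | 7.7 | 0.565 |
| 90% | 5.4 | 0.472 |

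The ratio is the looser margin below 80% and the stricter one above it.

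**5. Same data, two verdicts (200 per arm, one-sided 95% limits).** For the ratio, the standard error of the log is √(1/d₁ + 1/d₂), with d the events per arm.

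- *Control 90%, experimental 87%.* The ratio is 0.757. With 20 and 26 events the lower limit is 0.46, or 0.53 under the longer follow-up in step 6, so it fails 0.63. The upper limit of the difference is 3.0 + 1.645 × √[(0.90×0.10 + 0.87×0.13)/200] × 100 = 8.2 points, so it passes 10.
- *Control 70%, experimental 66%.* The ratio is 0.858. With 60 and 68 events the lower limit is 0.64 (0.68 with longer follow-up), so it passes 0.63. The upper limit of the difference is 11.7 points, so it fails 10.

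**6. Power of the hazard-ratio rule (equal arms, 200 per arm).** Power = Φ(√events / 2 × 0.462 − 1.645), where 0.462 = −ln 0.63.

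- *Two years each, 80% control.* 400 × 0.20 = 80 events; Φ(2.066 − 1.645) = 0.66.
- *Follow-up uniform on two to six years, constant hazard, no loss or deaths, 80% control.* λ = −ln(0.80)/2 = 0.1116. Events per arm = 200 × [1 − (0.800 − 0.512)/(4 × 0.1116)] = 71, about 142 in all. The formula gives 0.866, and simulation under the same assumptions gave 86%.
- *90% control.* Power is 0.43 with 40 events (two years each) and 0.64 with about 75 events (two to six years). The 10-point rule would have 0.95.

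**The case against.** The best defence is that section 6 contains one decision rule. The analysis text specifies a hazard-ratio test and explains its margin in the same sentence; the sample-size text restates one planning scenario in rates. Nothing proposes a test against a 70% floor or of a Kaplan-Meier difference. Much of this stands. The 70% is best read as loose wording for 80% minus 10 points, so a reader who counts three competing rules goes too far. What the defence does not remove is that the sample-size text says non-inferiority is defined by the 10-point difference, and uses that difference to derive the sample size and power.

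It can also be said that the direction of the ratio is clear enough. That is largely right. Only control over experimental turns 80% versus 70% into 0.63 and makes a limit above the margin sensible. A reader might infer that the rule would accept a harmful arm, because under the opposite convention a true ratio of 1.59 with about 100 events would lie above 0.63 with probability about 0.999. That reading ignores the protocol's own parenthesis. The unstated direction is an omission to repair; the arithmetic is not wrong.

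Finally, an SAP not at hand may name the governing rule. But the protocol has already fixed both statements, so an SAP that adopts one would contradict the other.

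**Conclusion.** The point holds as a conflict between the stated test and the stated definition, and between the stated test and the stated power. The margins agree at an 80% control rate and diverge on either side, from 13.2 points allowed at 70% control to 5.4 at 90%. The 80% power is correct for the difference. For the hazard-ratio test with equal arms at 80% control, it is about 66% with two years' follow-up each and about 86 to 87% under the favourable two-to-six-year assumptions. The trial is therefore not necessarily underpowered; the answer depends on an event count that the protocol does not give. The figures assume proportional hazards, and the longer-follow-up case also assumes uniform accrual, constant hazard and no deaths or losses.

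Two stronger inferences are not supported.

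- A reader might conclude from the five-year local control of 93% and 95% cited in the Introduction that the control arm will do far better than 80%. The same section reports conflicting data on margin and dose, and the protocol admits patients with microscopically positive margins. Those series show that 80% is uncertain; they do not establish another rate.
- In simulations with equal arms and two to six years' follow-up, the two tests disagreed in about a third of trials at 90% control. That cannot all be put down to the margins, because they already disagreed in about 15% at 80% control, where the margins coincide. The rest of the disagreement comes from the different estimators and follow-up windows.

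**What to change.** In Protocol section 6:

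1. Keep the hazard ratio as the only decision rule and state its direction: either control over experimental with the lower one-sided 95% limit above 0.63, or, equivalently, experimental over control with the upper limit below 1.59.
2. Replace the sentence that sets a margin of 70%, and the one that defines non-inferiority as a 10% difference, with a statement that 80% versus 70% at two years is what this hazard ratio corresponds to if the control rate is 80%.
3. Restate the power for the hazard-ratio rule, with the expected number of events and the follow-up assumed. About 116 events are needed for 80%.
4. Report the two-year Kaplan-Meier difference with its confidence interval as supportive.

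This needs no new data or assessments, but it is more than a wording change. Once the 10-point definition goes, the 198 per arm no longer supports the power statement, which has to be derived again. The stated power becomes less favourable if follow-up is only two years or if the control arm does better than 80%, and the text should say so.
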